### **7.5.2. ORR by Investigator**

The ORR per RECIST 1.1 by Investigator will be analyzed as described in [Section 7.5.1](#) above, respectively. The ITT and PITT populations will be used.

### **7.5.3. Duration of Objective Response (DOR)**

Duration of objective response (DOR) is defined as the time from the first documentation of objective response that is subsequently confirmed at a visit that is  $\geq 28$  days later to disease progression or death due to any cause.

$$\text{Duration of response (months)} = (\text{earliest date of PD or death due to any cause or censoring} - \text{date of first objective response} + 1)/30.4375$$

The DOR will be computed only among subjects who experience an objective response (confirmed CR or confirmed PR). The DOR will be analyzed and presented separately per BIRC and per Investigator for subjects in the ITT and PITT populations. The dates of progression and

censoring for DOR are shown in [Table 8](#) (see column PFS-EP-1 per BIRC and column PFS-EP-3 per Investigator).

The DOR will be analyzed using the same analysis method (Kaplan-Meier) as for the analysis on PFS (see [Section 7.1.5](#)).

#### **7.5.4. PFS by Investigator**

The analysis of PFS per RECIST 1.1 per Investigator is described in PFS-EP-3 in [Section 7.1.6](#), and will be conducted on subjects in the ITT and PITT populations.

#### **7.5.5. PFS and ORR per RECIST 1.1 by BIRC according to PD-L1 status**

Tumor markers such as PD-L1 will be measured at baseline on tumor specimen samples.

Analysis of PFS and ORR per RECIST 1.1 by BIRC will be performed by PD-L1 status ( $\geq 1\%$ ,  $< 1\%$ , Indeterminate) as defined in [Section 7.5.8](#). The analyses will be conducted by methodology described in [Section 7.1.5](#). Similar analyses may be undertaken for MET status (High/Positive or Low/Negative) using a  $\geq 50\%$  cutoff of tumor cell membrane staining and intensity score of 2+ or greater. The analysis will be conducted on subjects in ITT and PITT populations.

#### **7.5.6. Pharmacokinetics (PK)**

Pharmacokinetics (PK) analyses are outside the scope of this plan. A separate PK analysis plan and PK report will be provided.

#### **7.5.7. Immunogenicity Assessments**

Blood samples will be obtained from all subjects in both arms for immunogenicity assessment (anti-drug antibodies [ADA] for nivolumab and ipilimumab) by validated immunoassays predose on W1D1, W14D1, W26D1, and FU-1 and FU-2 visits. Immunogenicity assessments for binding antibody will utilize a tiered based approach. First, the screening assay will be performed for all available samples. Positive screening samples will be further confirmed for the ADA status. Positive samples from the confirmatory assay will be subsequently tested for titer. Neutralizing antibody assay may be applied if deemed necessary. The relationship between nivolumab and/or ipilimumab exposure and the status of ADA (binding) will be explored. A separate ADA analysis plan and ADA report will be provided.

#### **7.5.8. Biomarkers**

Biomarkers such PD-L1 expression, MET and other select ones will be summarized. For assessment of PD-L1 expression, evaluation of at least 100 viable tumor cells is required.

Positive staining is defined as  $\geq 1\%$  and negative is defined as  $< 1\%$  of cells that exhibit circumferential and/or partial linear plasma membrane staining at any intensity. High cytoplasmic staining can interfere with membrane scoring and will define as indeterminate. Additionally, failure of PD-L1 staining due to suboptimal tissue sample integrity or assay failure will also be defined as indeterminate.

Baseline and percent changes from baseline for select biomarkers may be summarized. Descriptive statistics may be presented by treatment group using all available data from protocol-defined time-points. Appropriate transformations may be applied to normalize the data for presentation or analysis.

A waterfall plot of best percentage change from baseline in respective biomarker will be presented for each treatment group using the ITT population. In all calculations, best change from baseline will be based only on protocol-defined time-points. Best change is defined as either the largest reduction or the largest increase depending on the directionality of the biomarker being summarized.

### **7.5.9. Health-Related Quality of Life (HRQOL)**

Health-related quality of life (HRQOL) will be assessed by the EuroQol Health questionnaire EQ-5D-5L (Reenen et al 2015). The questionnaire will be self-completed by the subjects at various time points regardless of whether study treatment was given, reduced, held, or discontinued until the date of the last tumor imaging assessment or the study met its primary endpoint and will provide a generic measure of health for clinical appraisal (see protocol Section 5.7.7). The EQ-5D-5L questionnaire has two pages: a descriptive page, which assesses on an increasing severity scale of 1 (no problems with function/no symptoms) – 5 (unable to perform function/extreme symptoms) changes in the following five dimensions: mobility, self-care, usual activities, pain/discomfort, and anxiety/depression. The second page has a 0-100 visual analogue scale (VAS), which records the subjects self-rated health between 100 (best health you can imagine) and 0 (worst health you can imagine) and serves as a quantitative measure of health by the subject (see protocol Appendix D and EQ-5D-5L User Guide 2015).

To compare the two treatment arms for subjects in the ITT population, the following summaries are planned at each time point for each of the 6 questions:

Within each treatment arm:

- Descriptive statistics (number of observations, mean and standard deviation)

- Rate of completion for the questionnaire at each time point. This is defined as total number of subjects who answered all questions on the EQ-5D-5L questionnaire / the expected total number of subjects still on study at the visit
- Mean change from baseline at each time point and the corresponding 95% CI and p-value from one-sample t-test
- Effect size for change from baseline within arm, calculated as (mean of change in score/pooled standard deviation for baseline scores). An effect size greater than  $\geq 0.3$  will be considered potentially clinically meaningful
- Shift in the severity scale since baseline

Across treatment arms

- The difference in the effect sizes will be presented
- Difference in mean change from baseline for the questions at the time point will be evaluated by a two sample t-test
- Line plots for mean  $\pm$  standard error and the corresponding mean for change from baseline over time. Data from both treatment arms will be displayed on the same plot. In addition, these plots will also show the average state of the subjects at 3 landmark points, namely, around end of treatment, around progression and around 30 days post-treatment follow-up for the two treatment arms
- Percentage of subjects in Level 1 (no problem) vs. Levels 2-5 (any problems) will be summarized over time
- Percentage of subjects with any problems (Level 2-5) will be compared between the treatment arms using a bar chart

The EQ-5D-5L may be converted into a single index (EQ-Index) value normalized across different countries where the index is validated. See [Appendix D](#) for conversion details. For EQ-VAS and EQ-Index, descriptive statistics for change from baseline at each time will be presented. Plots for mean  $\pm$  standard error and mean change from baseline  $\pm$  standard error over all time points for the two treatment arms will be generated. In addition, repeated-measures mixed-effects models will be used to explore treatment differences over time. These analyses will include the outcome variable of QOL score change from baseline. The predictors (fixed effects) will be the baseline scores, treatment arms, visit, and randomization strata described in [Section 2.5](#). The individual subject nested within the planned treatment arm will be the random effect. All available data will be included for the analysis. The estimated least squares means for the two treatment arm and their difference, the p-values comparing the 2 treatment arms and the

effect size will be presented. No adjustment will be made for multiple comparisons. An effect size of difference  $\geq 0.3$  will be considered potentially clinically meaningful. All summaries will be provided for the ITT population.

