#### **5.7.7 Health-related Quality of Life Assessments**

Health-related quality of life (HRQOL) assessments will be performed using the EuroQol Health questionnaire instruments EQ-5D-5L. This is a standardized instrument for use as a measure of self-reported general health status. The EQ-5D-5L comprises 5 dimensions (mobility, self-care, usual activities, pain/discomfort, and anxiety) and a visual analog rating scale (VAS) ([Appendix I](#)). The utility data generated from EQ-5D assessments are recommended for and commonly used in cost effectiveness analysis. The first assessment will be at Screening within 14 days prior to randomization. Assessment will be collected every 3 weeks after randomization until W10D1 and every 4 weeks thereafter. Subjects will continue completing questionnaires regardless of whether study treatment is given, reduced, held, or discontinued until the date of the last tumor imaging assessment or the study meets its primary endpoint. Consequently, these assessments may be required in the Post-Treatment Period for some subjects ([Appendix A](#)).

Subjects are to complete the questionnaires prior to each clinic visit. If a clinic visit is not possible, subjects should complete the questionnaires as per schedule and return it to the site either during the next visit or send it to the site by fax or postal mail. Ideally, study subjects should not receive any information about their most recent medical results prior to completing the questionnaires in order to ascertain that their reporting not be influenced by such information

CONFIDENTIAL

when completing the questionnaires. At clinic visits, questionnaires should be carefully reviewed by the study staff at the site for completeness.

Subjects who are not compliant with completing the questionnaires should be reminded by the Investigator that these reports are an essential part of the study and timely completion is required.

Every effort should be made by the study site to retrieve all HRQOL questionnaires, including the assessment following radiographic progression or discontinuation of study treatment, and to keep them at the site as source documentation.

Translated copies of the EQ-5D-5L questionnaires, if required, and instructions for filling them out will be provided to each study site in a separate study manual.

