## 2.5. Randomization and Blinding

Randomization will be stratified by the following factors established at screening:

- IMDC prognostic score (1-2 risk factors [intermediate] vs 3-6 risk factors [poor])
- Region ([US or Canada or Europe or Australia or New Zealand] vs [Latin America or Asia])

The IMDC risk factors are (Heng et al 2009):

- KPS < 80%
- Less than 1 year from initial RCC diagnosis (including original localized disease if applicable) to systemic treatment
- Hemoglobin (g/L) < lower limit of normal (LLN)
- Corrected calcium (mg/dL) > 10 mg/dL
- Absolute neutrophil count (ANC) (G/L) > upper limit of normal (ULN)
- Platelet count ( $10^9/L$ ) > ULN

This is a double-blinded study. The cabozantinib-matched placebo will be given in combination with nivolumab and ipilimumab in the control arm to blind (mask) study treatment. The

assignment of study treatment will be unknown to the subjects, Investigators, study centers, Sponsor, and any clinical research organization (CRO) affiliated with the study other than those authorized to access treatment assignment for regulatory safety reporting and submission processes (see Protocol Section 8.2.2), Interactive Voice/Web Response System (IxRS) system administration, and drug supply management.

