## 7.5. Additional Endpoints

Each exploratory endpoint will be analyzed using an appropriate two-sided statistical test without adjustment for multiplicity unless specified otherwise. Statistical results for exploratory endpoints will be considered supportive. Exploratory analyses will be performed on the ITT population unless specified otherwise.

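### The five EQ-5D-5L dimension items are compared between arms only by an unadjusted t-test on change, although the same SAP section adjusts EQ-VAS and EQ-Index for baseline score and randomization strata

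*SAP*

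**What the plan says.** SAP 7.5.9 states its item-level scope as "the following summaries are planned at each time point for each of the 6 questions". The six questions are the five dimensions, each scored 1 to 5, and the 0–100 visual analogue scale (VAS). The between-arm test for them is "Difference in mean change from baseline for the questions at the time point will be evaluated by a two sample t-test". The other between-arm item displays are differences in effect size, line plots, and percentages or a bar chart of Level 1 against Levels 2–5. None of these adjusts for baseline or strata.

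A later paragraph of the section turns to the two summary measures: "For EQ-VAS and EQ-Index, descriptive statistics for change from baseline at each time will be presented". It then adds repeated-measures mixed models of change from baseline and says of them: "The predictors (fixed effects) will be the baseline scores, treatment arms, visit, and randomization strata". The five dimension items are not named there.

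The covariates are available. On the baseline questionnaire, Protocol 5.7.7 says: "The first assessment will be at Screening within 14 days prior to randomization". On the strata, SAP 2.5 says: "Randomization will be stratified by the following factors established at screening"; they are IMDC score (intermediate or poor) and region (two levels).

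On status, SAP 7.5 says: "Each exploratory endpoint will be analyzed using an appropriate two-sided statistical test without adjustment for multiplicity unless specified otherwise". It treats exploratory results as supportive, and SAP 7.3 treats p-values outside the primary and secondary endpoints as descriptive.

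**The concern.** A change score subtracts the whole baseline value. The most precise linear adjustment subtracts only the part that predicts follow-up, that is, the regression slope b = r × (follow-up SD / baseline SD) times baseline. Unless b equals 1, the change score carries extra noise, and a chance difference between arms at baseline is left partly uncorrected or over-corrected. The t-test also makes no use of the two stratification factors, which the SAP uses both in its primary PFS test (7.1.5) and in its own EQ-VAS and EQ-Index model.

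At stake is the precision of the item-by-visit contrasts, mainly at later visits. Questionnaires stop at the last tumor imaging assessment or when the study meets its primary endpoint, so fewer forms can be expected there.

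**Working it through.** The documents give no HRQOL sample size, power, SD or correlation, so there is no planned figure to reproduce.

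**Inputs**
- From SAP 2.4: 420 subjects per arm.
- From SAP 7.5.9: an effect size of 0.3 is potentially clinically meaningful.
- Assumed: r = 0.3, 0.5, 0.7; k = follow-up SD / baseline SD = 1 or 1.3; two-sided 5%, because 7.5.9 states no alpha; 100 completers per arm as an illustration of a late visit.

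**Variances, in units of baseline SD squared**
- Change score: Vc = 1 + k² − 2rk.
- Baseline-adjusted: Va = k²(1 − r²).
- Difference: Vc − Va = (1 − rk)². This is never negative, and it is zero when rk = 1.
- With k = 1 the ratio Va/Vc simplifies to (1 + r)/2.

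| k | r | Vc | Va | Va/Vc | CI narrower by |
|---|---|---|---|---|---|
| 1 | 0.3 | 1.40 | 0.91 | 0.65 | 19.4% |
| 1 | 0.5 | 1.00 | 0.75 | 0.75 | 13.4% |
| 1 | 0.7 | 0.60 | 0.51 | 0.85 | 7.8% |
| 1.3 | 0.3 | 1.91 | 1.538 | 0.81 | 10.3% |
| 1.3 | 0.5 | 1.39 | 1.268 | 0.91 | 4.5% |
| 1.3 | 0.7 | 0.87 | 0.862 | 0.99 | 0.5% |

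The last column is 1 − √(Va/Vc). A k below 1 would make the gain larger.

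**Chance imbalance.** If the arms differ at baseline by d, the change-score contrast is off by (rk − 1)d, given that imbalance. With n per arm, d has standard error √(2/n), which is 0.069 SD at 420 and 0.141 SD at 100. For k = 1 and r = 0.3 the typical error is 0.7 × 0.069 = 0.048 SD and 0.7 × 0.141 = 0.099 SD respectively. This is the same loss as in the table, seen conditionally on the imbalance; it is not a second one.

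**Power for a difference of 0.3 baseline SD**, from Φ(0.3/√(2V/n) − 1.96), t-test against adjusted:

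| k | r | 420 per arm | 100 per arm |
|---|---|---|---|
| 1 | 0.3 | 95.7% / 99.5% | 43.4% / 60.4% |
| 1 | 0.5 | 99.2% / 99.9% | 56.4% / 68.8% |
| 1 | 0.7 | about 100% both | 78.2% / 84.4% |
| 1.3 | 0.3 | 88.2% / 93.9% | 33.5% / 40.2% |
| 1.3 | 0.5 | 95.8% / 97.1% | 43.6% / 47.0% |
| 1.3 | 0.7 | 99.7% both | 62.3% / 62.7% |

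**Ordinal check.** A five-level item was simulated with 100 per arm and 2000 replicates at latent correlations 0.3, 0.5 and 0.7. The standard-error ratios, adjusted to unadjusted, were 0.82, 0.87 and 0.93, with power 33% vs 46%, 44% vs 53% and 59% vs 64%. The item-level correlations were 0.24, 0.41 and 0.60, for which √((1 + r)/2) gives 0.79, 0.84 and 0.89. The simulated gain is slightly smaller than that because the treatment shift raised the item's follow-up SD above its baseline SD. The gain therefore survives a coarse scale but is sensitive to k.

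**Strata.** The documents give no stratum effect on EQ-5D, so this part of the gain cannot be computed.

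**The case against.** The strongest reply is that nothing here is wrong, only less efficient. Randomization makes the change-score t-test unbiased. It sits in a list of summaries for an exploratory endpoint, its p-values are descriptive, and HRQOL has no sample-size target. All of that stands, and it limits the point to a refinement.

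Four stronger readings are tempting, and the documents do not support them.
- *The baseline is thrown away.* A change score uses the baseline; only the remaining gain from regression adjustment is lost.
- *HRQOL as a whole lacks adjustment.* VAS is one of the six questions and already has the adjusted mixed model. So does EQ-Index, which is built from the five dimensions (SAP Appendix D), although its derivation is optional.
- *Tolerability conclusions rest on these tests.* SAP 8 assesses safety and tolerability through adverse events, laboratory values, vital signs and performance status; EQ-5D-5L is not listed. Protocol 5.7.7 describes it as a general health measure with use in cost-effectiveness work.
- *Intervals would be 8–19% narrower.* That range requires equal SDs. At k = 1.3 and r = 0.7 the narrowing is about 0.5%.

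The baseline form is also scheduled for every subject rather than guaranteed; SAP 7.5.9 plans completion rates. Adjustment would not address multiplicity across items and visits either.

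**Conclusion.** The point holds for the five dimension items. Their only planned between-arm test ignores the strata and uses the baseline less efficiently than the model given to EQ-VAS and EQ-Index in the same section. Adjustment multiplies the variance by 0.65–0.85 with equal SDs, or by about 0.81–0.99 with a follow-up SD 1.3 times baseline, for assumed r of 0.3–0.7. Both r and the SD ratio are assumptions, and the strata component is unknown. Near full completion the effect on power for 0.3 SD is small: the planned test already has 88% or more in every case shown. The loss is larger at visits with few completers. Severity is nice-to-have: no primary or secondary conclusion changes, and no result would be invalid if the plan stayed as it is.

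**What to change.** In SAP 7.5.9, replace the item t-tests for the five dimensions with a model containing arm, baseline item score and the two randomization strata, and report the adjusted difference with its 95% CI. Either route works:
- Extend the mixed model already planned for EQ-VAS and EQ-Index. Its listed fixed effects include no arm-by-visit term, so add one if a difference at each visit is wanted.
- Fit an ANCOVA at each visit.

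Keep raw means and SDs as description, and leave VAS to its existing mixed model so that it does not acquire a second adjusted estimate.

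The cost is about one SAP sentence and a different SAS procedure. No new data are needed. The trade-off is that the tables show adjusted rather than raw differences, and a linear model on a 1–5 item remains an approximation, as the t-test is now.

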#### **7.5.10. Health Care Resource Utilization**

For this study the following health care resource utilization (HCRU) parameters collected during the study observation period will be summarized for subjects in the ITT population:

- Days of hospitalization due to SAEs
- Days in intensive care unit (ICU) due to SAEs
- Number of emergency room (ER) visits due to SAEs
- Number and type of surgeries
- Number and type of transfusions

The summaries will include:

- Number and percentage of subjects in each category of HCRU
- Descriptive statistics for each HCRU category amongst those subjects who utilized the respective resource
- Total number of days or visits as applicable for each HCRU
- Per person year summary for each HCRU

To calculate the per person year value for a subject for a HCRU parameter, the numerator is the sum of the days or visits for that subject for the parameter; and the denominator is defined as:  $(\text{safety observation period} - \text{date of randomization} + 1) / 365.25$ .

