### **5.7.8      Health Care Resource Utilization**

Health care resource utilization parameters will be collected from randomization through the FU-2 visit. These include hospital admissions, emergency room visits, intensive care unit admissions, length of stay, surgeries, and transfusions.

These data will not be collected in the Maintenance Phase.

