- Any SAEs assessed as related to study treatment or study procedures, even if the SAE occurs more than 100 days after the date of the decision to permanently discontinue study treatment.

Note: If the subject does not meet the eligibility criteria during screening, then SAEs only need to be reported from the time the subject signs the informed consent until the day when the subject has been determined to not be eligible for study participation.

SAEs that occur after the initial consent and through 100 days after the date of the decision to permanently discontinue study treatment must also be recorded on the CRF page.

The minimum information required for SAE reporting includes identity of investigator, site number, subject number, and an event description. Other important information requiring timely reporting are the SAE term(s), the reason why the event is considered to be serious (ie, the seriousness criteria), and the Investigator's assessment of the relationship of the event to study treatment. Additional SAE information including medications or other therapeutic measures used to treat the event, action taken with the study treatment because of the event, and the outcome/resolution of the event will be recorded on the SAE form.

In all cases, the Investigator should continue to monitor the clinical situation and report all material facts relating to the progression or outcome of the SAE. Furthermore, the Investigator may be required to provide supplementary information as requested by the Sponsor's Drug Safety personnel or designee.

When reporting SAEs, the following additional points will be noted:

- When the diagnosis of an SAE is known or suspected, the Investigator will report the diagnosis or syndrome as the primary SAE term, rather than as signs or symptoms. Signs and symptoms may then be described in the event description.
- Death will not be reported as an SAE, but as an outcome of a specific SAE, unless the event preceding the death is unknown. Terms of "Unexplained Death" or "Death from unknown origin" may be used when the cause is unknown. In these circumstances the cause of death must be investigated and the diagnosis amended when the etiology has been identified. If an autopsy was performed, the autopsy report should be provided.

CONFIDENTIAL

Protocol XL184-313 Protocol Amendment 3.0  
Page 119 of 193

- While most hospitalizations necessitate reporting of an SAE, hospitalizations that do not require SAE reporting are as follows:

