  - Elective or previously scheduled surgeries or procedures for preexisting conditions that have not worsened after initiation of treatment (eg, a previously scheduled ventral hernia repair). SAEs must, however, be reported for any surgical or procedural complication resulting in prolongation of the hospitalization.
  - Prespecified study hospitalizations for observation.
  - Events that result in hospital stays of less than 24 hours and that do not require admission (eg, an emergency room visit for hematuria that results in a diagnosis of cystitis and discharge to home on oral antibiotics).
- SAEs must be reported for any surgical or procedural complication resulting in prolongation of the hospitalization.

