### **4.5.1. Standard Period**

The standard safety observation period is the interval from the first dose date of study treatment to the earliest of:

- Date of last dose of last component of study treatment + 30 days, or
- Date of death, or
- Date subject withdrew consent for non-interventional study assessments, or
- Data cutoff date for analysis under consideration.

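### The utilization summary counts ER visits, hospital days and ICU days only when due to SAEs, which would miss most treat-and-discharge ER visits, and its per-person-year window is not defined

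*SAP*

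**What the plan says.** Protocol 5.7.8 defines the endpoint broadly: "These include hospital admissions, emergency room visits, intensive care unit admissions, length of stay, surgeries, and transfusions". On timing it says "Health care resource utilization parameters will be collected from randomization through the FU-2 visit". Neither sentence mentions SAEs.

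SAP 7.5.10 is narrower. Its ER row reads "Number of emergency room (ER) visits due to SAEs", and the rows for hospital days and ICU days carry the same restriction. Surgeries and transfusions, in the same list, do not.

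Protocol 8.2.1 introduces a list of exemptions with "While most hospitalizations necessitate reporting of an SAE, hospitalizations that do not require SAE reporting are as follows". One entry is "Events that result in hospital stays of less than 24 hours and that do not require admission", illustrated by an ER visit that ends in discharge home on oral antibiotics.

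On the window, SAP 7.5.10 says that "parameters collected during the study observation period will be summarized for subjects in the ITT population". The per-person-year denominator is written as the safety observation period minus the randomization date plus 1, divided by 365.25. SAP 4.5 defines two such periods, both starting at first dose. The standard one can run to "Date of last dose of last component of study treatment + 30 days". The extended one, introduced for AESIs, can run to 100 days after last dose. Either stops earlier at death, withdrawal of consent for non-interventional assessments, or data cutoff.

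**The concern.** Two separate matters are at stake.

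The first is coverage. An ER visit that ends in discharge is a plain case of resource use, and the protocol collects it. If the table counts only SAE-related visits, and such a visit ordinarily needs no SAE report, the ER row no longer measures what the protocol set out to describe. The SAP gives no reason for narrowing three of its five rows.

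The second is the rate. A per-person-year figure needs events and time taken over the same window. Here the numerator uses a period that SAP 4.5 and 7.5.10 do not define, and the denominator uses a period of which the SAP has two. Two programmers could produce different tables from the same data. The population is ITT, which includes subjects who were never dosed, and for them neither safety period exists.

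**Working it through.** The plan states no rate, power or other figure for this endpoint, so there is nothing to reproduce. The coverage question is settled by comparing sections, and the window question by simple arithmetic.

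**Coverage**

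- Collected (Protocol 5.7.8): admissions, ER visits, ICU admissions and length of stay, whether or not an SAE is involved.
- Summarized (SAP 7.5.10): hospital days, ICU days and ER visits only if due to an SAE.
- Needs no SAE report on hospitalization grounds (Protocol 8.2.1): stays under 24 hours without admission, elective or previously scheduled procedures, and prespecified observation stays.
- Still an SAE (Protocol 8.2.1): an event that is life-threatening, incapacitating or an important medical event, even without hospitalization.

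The ordinary treat-and-discharge ER visit is therefore collected but not summarized. Most true admissions do generate an SAE report, so hospital and ICU days should lose little.

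**Window**

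Inputs: FU-2 at 100 ± 14 days (Protocol 3.3), so day 86 to 114; period ends at +30 and +100 days (SAP 4.5.1 and 4.5.2); 30.4375 days per month (SAP 4); average time on treatment of 12 to 18 months (Protocol 3.2).

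Let d be days on treatment. If events are counted to FU-2 at day F, the reported rate divided by the rate that uses the same window for events and time is:

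- standard period: (d + F)/(d + 30)
- extended period: (d + F)/(d + 100)

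| Months | d | Standard, F = 100 | F = 86 to 114 | Extended, F = 100 | F = 86 to 114 |
|---|---|---|---|---|---|
| 3 | 91.3 | 191.3/121.3 = 1.58 | 1.46 to 1.69 | 1.00 | 0.93 to 1.07 |
| 6 | 182.6 | 282.6/212.6 = 1.33 | 1.26 to 1.40 | 1.00 | 0.95 to 1.05 |
| 12 | 365.3 | 465.3/395.3 = 1.18 | 1.14 to 1.21 | 1.00 | 0.97 to 1.03 |
| 18 | 547.9 | 647.9/577.9 = 1.12 | 1.10 to 1.15 | 1.00 | 0.98 to 1.02 |

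The standard period ends 100 − 30 = 70 days before nominal FU-2 (56 to 84 with the visit window). At 12 months, person-time is 395.25/365.25 = 1.082 years with the standard period and 465.25/365.25 = 1.274 years to FU-2.

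Assumptions: first dose on the day of randomization, discontinuation decision on the day of last dose, and follow-up to FU-2 without earlier death, withdrawal or cutoff. The +1 day is ignored. The ratio compares two denominators under the same count, so it does not require a constant event rate.

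**The case against.** There is a fair case that this is analyst's choice. Protocol 9.2.4 leaves the analysis of additional endpoints to the SAP, and the three rows openly say that they are limited to SAEs. The CRF is not available to us, so data on non-SAE ER visits may not exist in a form that can be summarized. That stands as a limit on the remedy. It does not remove the gap between what the protocol says is collected and what the SAP counts.

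Three stronger readings are tempting, and the documents do not support them.

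- A reader might infer that ER visits without admission count as zero. They do not: the exemption concerns the hospitalization route to seriousness, and a visit for an event that meets another criterion is still due to an SAE.
- A reader might infer that the rates are inflated. That needs the +30-day period together with counts that run to FU-2. The standard period is a plausible reading, because it is the SAP's default for AE summaries and the extended one was written for AESIs. But the SAP does not say so, and elsewhere (for example 8.7.2 and 8.8.2) it names the period it means. If both counts and time stopped at +30 days, the rate would be consistent but would discard data collected up to FU-2.
- A reader might infer a biased comparison between arms. The inflation would differ by arm only if time on treatment did, and the documents give no time on treatment by arm.

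The awkward subtraction of a date from a period is a wording lapse; the end date of the period is clearly meant.

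**Conclusion.** The point holds as a minor one. The SAE restriction would undercount ER use as the protocol defines it. The documents give no number of visits, so the undercount cannot be sized. That most treat-and-discharge visits drop out follows from the protocol's own example and assumes that few of them meet another seriousness criterion.

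The window is unspecified in three respects: the numerator period, the choice of safety period, and never-dosed subjects. These gaps exist whichever period was intended. Inflation is conditional. For subjects followed to FU-2 it would be about 1.12 to 1.18 over the expected 12 to 18 months on treatment, with larger values such as 1.58 only for those who stop at about 3 months. For a subject whose observation ends before +30 days, or who is still on treatment at cutoff, the ratio is 1. Under the extended period it is about 1.00, provided that the decision date and last dose coincide; FU-2 is timed from the later of the two, whereas the safety periods run from last dose.

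Utilization is a descriptive additional endpoint, so nothing here touches the PFS or OS tests.

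**What to change.** In SAP 7.5.10:

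1. Summarize all collected ER visits, admissions, hospital days and ICU days, with SAE-related use as a sub-row. If the CRF captures these items only for SAEs, state that non-SAE use is not captured.
2. Use one window for numerator and denominator: randomization to the earliest of FU-2, death, withdrawal or data cutoff. Drop the reference to the safety observation period.
3. For never-dosed subjects, count person-time only while utilization data were actually collected, or leave them out of the rate and list them separately. Running their time to last contact would not do. Under Protocol Appendix A they are contacted every 12 weeks for survival and subsequent anticancer treatment, and utilization is not scheduled at those contacts, so this would add time in which no use could be recorded.

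The cost is a few lines of SAP text and one extra row per table. No new data collection, protocol amendment or change to sample size or alpha is needed.
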